12.2.4 Analysis of Imaging/Fluid Biomarker Efficacy Outcomes

The imaging/fluid biomarker endpoints listed in [Section 4.2](#) will be analyzed using both the LME model and the MMRM as specified in SAP [Sections 12.1.6.8](#), [12.1.6.9](#), and [12.1.7](#), except that separate models will be fitted to independently estimate the treatment effect of each drug. When the fluid biomarkers of the direct placebos are processed using different assays for each study drug, the direct placebos will not be pooled; when the fluid biomarkers of the DIAN-OBS eligible subjects are processed using different assays than those used in the DIAN-TU-001, the DIAN-OBS eligible subjects will not be pooled.

Because some of the subjects were only given the tau PET scan after the administration of the study drug, they do not have a baseline tau PET endpoint. Thus, only the LME model will be used for tau PET endpoint analysis.

For some fluid biomarker outcomes, the eligible DIAN-OBS subjects' data are not combinable or not available at all (see SAP [Section 4.2.4](#) for details). For these outcomes, neither the LME model nor the MMRM will include DIAN-OBS data.

Any analyses that will be conducted for the fluid biomarkers that will be processed using ELISA will not include the gantenerumab active drug arm.

12.2.5 Analysis of Other Additional Analysis Endpoints

For "Other Additional Analysis Endpoints" listed in SAP [Section 4.2.5](#), both the LME model and the MMRM will be used to analyze these efficacy endpoints, unless alternative methods are specified. And these models will be set up as specified in SAP [Sections 12.1.6.8](#), [12.1.6.9](#), and [12.1.7](#) in terms of model setup and the corresponding analysis population. For any endpoint, if no data or very limited data are available from DIAN-OBS, then the eligible DIAN-OBS subjects will

not be included in these analyses. Some of these analyses may not be included in the CSR and may be documented separately.

12.3 The Procedure to Conduct All the Analyses Using the Cognitive MDPM/UDPM

12.3.1 The Rationale for Outlining the Procedure

The cognitive MDPM/UDPM is a novel statistical model jointly developed by DIAN-TU-001 and [REDACTED]. We outline the following strict operational procedure for the conduct of statistical analyses at the end of the study.

12.3.2 The Procedure

12.3.2.1 Development of the cognitive MDPM/UDPM analytical package

The cognitive MDPM/UDPM packages for any analyses listed in SAP [Section 11](#) will be provided by [REDACTED] using Fortran computer language.

12.3.2.2 Validation of the cognitive DPM package

The Fortran code for the cognitive MDPM/UDPM will be validated by internal statisticians from both DIAN-TU and [REDACTED]. Statisticians from [REDACTED] will test all the cognitive MDPM/UDPM packages provided by [REDACTED] based on simulated data and convey any potential problems to DIAN-TU and [REDACTED]. If warranted, the cognitive MDPM/UDPM packages will be edited and then validated again. This iteration will continue until the three parties ([REDACTED], DIAN-TU, and [REDACTED]) agree with the final version of the cognitive MDPM/UDPM packages. The final version of the cognitive MDPM/UDPM packages will be sent to the U.S. Food and Drug Administration as the statistical model for the DIAN-TU-001 study.

12.3.2.3 Conduct of all the analyses using cognitive DPM package

[REDACTED] will use the finalized MDPM/UDPM packages to conduct the primary, secondary, subgroup analyses, and sensitivity analyses, and to prepare the final report of the trial results. The exploratory analyses using the MDPM/UDPM packages can be conducted by DIAN-TU-001 or [REDACTED].

12.4 Exploratory Analyses

The following analyses will be conducted for the combined population of the mITT population and the eligible DIAN-OBS subjects unless otherwise specified.

12.4.1 Exploratory Study Endpoints

Exploratory study endpoints include clinical, cognitive, and biomarker measures as listed in SAP [Section 4.2.5](#) which are not designated as primary or secondary, or those endpoints designated in each drug-specific appendix.

12.4.2 Statistical Analyses of the Exploratory Study Endpoints

The exploratory study endpoints will be summarized by descriptive statistics for each visit by treatment. The difference between the active drug arm and the corresponding reference group will be tested by a chi-squared or Fisher's exact test (when the number of observations in any cell is less than 5) if the exploratory endpoint is a categorical variable, or by LME model and the MMRM as defined in [Sections 12.1.6.8](#), [12.1.6.9](#), and [12.1.7](#) if the exploratory endpoint is continuous.

12.4.3 Other Exploratory Analyses

12.4.3.1 Analysis of the combination of the active drug arms

The following analysis will be conducted for the combined population of the mITT population and the eligible DIAN-OBS subjects.

When neither drug's primary efficacy analysis is significant, the active solanezumab drug and the active gantenerumab drug will be pooled together as a single active drug arm. The MDPM will be used to analyze the pooled, single active drug arm, the mutation positive placebo arm, and the eligible DIAN-OBS subjects arm. The parameters of the MDPM will be set up similarly to SAP [Section 12.1.3](#).

12.4.3.2 Analysis to evaluate the treatment effect on each component of the alternative multivariate endpoint and of the Cogstate multivariate endpoint

The following analyses will be conducted for the combined population of the mITT population and the eligible DIAN-OBS subjects.

In the primary analysis, three CPRs (denoted as e^{θ_2} , e^{θ_3} and e^{θ_4} in [Section 12.1.3](#)) are used to model the cognitive progression for the mutation positive placebo arm, the active gantenerumab drug arm, and the active solanezumab drug arm across the four components in reference to the eligible DIAN-OBS subjects arm. Instead of using the same θ for all four components, different θ s will be used for each component. Specifically, $e^{\theta_{21}}$, $e^{\theta_{22}}$, $e^{\theta_{23}}$, and $e^{\theta_{24}}$ will be used to estimate the cognitive progression ratios for the four components between the mutation positive placebo arm and the eligible DIAN-OBS subjects arm; $e^{\theta_{31}}$, $e^{\theta_{32}}$, $e^{\theta_{33}}$, and $e^{\theta_{34}}$ between the active gantenerumab drug arm and the eligible DIAN-OBS subjects arm; and $e^{\theta_{41}}$, $e^{\theta_{42}}$, $e^{\theta_{43}}$, and $e^{\theta_{44}}$ between the active solanezumab drug arm and the eligible DIAN-OBS subjects arm. The CPRs for each component for each active drug arm compared to the mutation positive placebo arm will be calculated based on these CPRs. For example, the CPR for the first component between the active gantenerumab and the mutation placebo arm will be calculated as $\frac{e^{\theta_{31}}}{e^{\theta_{21}}}$.

Additionally, the univariate DPM will be applied to each component separately to estimate the treatment effect on each component. The univariate DPM will be set up similarly to that in [SAP Section 12.1.9](#).

12.4.3.3 Analysis to incorporate covariates

Demographics and baseline measures including categorical measurements of sex, APOE status, and continuous measurement of baseline CDR-SB, age, and years of education, will be compared between the mutation positive placebos and the eligible DIAN-OBS subjects using analysis of variance, Pearson chi-squared test or any other test as deemed appropriate. If the difference in a given variable is significant at a 5% two-sided type I error rate, then this variable will be added to the MDPM for the sensitivity analysis. In general, to add a covariate to the model we take the following steps.

- A) For a binary covariate, we label the more common outcome as 0 and the less common outcome as 1.
- B) For an unordered categorical variable, we label the most common outcome as 0 and create an indicator (binary) variable for each other possible outcome.
- C) For an ordered categorical variable, we label the most common extreme outcome (smallest or largest) as 0 and create an indicator (binary) variable for each other possible outcome.

D) For a continuous covariate, we first normalize the variable by subtracting the mean and dividing by the standard deviation of the variable for each model fit.

We label a generic covariate as Z_{ij} . The primary analysis is based on the following mean and variance structure:

$$Y_{ij} = \gamma_i + g(E_{ij}|\delta_i, \theta) + \epsilon_{ij} \text{ for } i = 1, \dots, k; j = 1, \dots, n_i.$$

When we add covariates, Z_{ij} , to the analysis we frame the modeling as

$$Y_{ij} = \gamma_i + Z_{ij}\beta + g(E_{ij}|\delta_i, \theta) + \epsilon_{ij} \text{ for } i = 1, \dots, k; j = 1, \dots, n_i.$$

For multiple covariates, Z_{ij1}, \dots, Z_{ijc} , the modeling is

$$Y_{ij} = \gamma_i + \sum_{c=1}^c Z_{ijc}\beta_c + g(E_{ij}|\delta_i, \theta) + \epsilon_{ij} \text{ for } i = 1, \dots, k; j = 1, \dots, n_i.$$

12.4.3.4 Subgroup/subset analyses for CDR-SB and FAS

CDR-SB and FAS will be analyzed using the models/population (mITT only, mITT and eligible DIAN-OBS subjects) specified in [Section 12.1.8](#).

13 SAFETY ANALYSES

Safety analysis will be based on the safety population. The eligible DIAN-OBS subjects who enrolled only in DIAN-OBS will not be included, and the data collected in the DIAN-OBS study for the DIAN-OBS run-in subjects will not be included.

The safety endpoints of the study include:

- Treatment exposure
- Adverse events (AEs)
- Amyloid-related imaging abnormalities (ARIAs)
- Clinical laboratory evaluations

- Vital signs
- 12-lead electrocardiogram (ECG)
- C-SSRS
- Safety MRIs
- Serious adverse events

If any safety endpoint is unique to a given drug due to the mode of drug administration, this safety endpoint will only be analyzed for this given drug and its direct placebos. These drug-specific safety endpoints will be listed in the drug-specific appendix.

13.1 Duration of Treatment

Duration of treatment (days) will be defined for each subject as

- Duration of treatment (days) = date of last dose – date of first dose +1.

Duration of treatment summarized as total days per patient will be presented by treatment using the descriptive statistics including mean (SD), 25th percentile, median, and 75th percentile.

The proportion and frequencies of incomplete infusions will be summarized by doses and compared between treatment arms.

The total number of administered doses (including both fully and partially administered) for each subject will be summarized by treatment arms and by dose levels within each active treatment arm using descriptive statistics.

13.2 Adverse Events

An AE is defined as any untoward medical occurrence in a clinical trial subject, whether it is considered to be drug related. AEs will be recorded and assessed as to whether they are treatment-emergent adverse events (TEAEs). TEAEs are defined as events that first occur or worsen (increase in severity) after the first dose of the study drug. The onset date/time of an AE will be compared to the date/time of first dose of the study drug to determine if the AE is treatment emergent or not. If the AE onset date is missing or partial, the date will be compared as far as possible with the date of first dose of the study drug. AEs will be assumed to be treatment-emergent unless there is clear evidence (through comparison of partial dates and/or collected assessment of

whether the AE started prior to the first dose of the study drug) suggesting the AE started prior to the first dose of study medication.

An overall summary of TEAEs will be presented with the number and percentage of subjects having a TEAE, a severe TEAE, a TEAE related to study treatment, a serious TEAE, a TEAE leading to study discontinuation, and a TEAE with an outcome of death. The overall summary will be presented for each study drug arm, the mutation positive placebo arm, and the mutation negative placebo arm. The summary will also be reported by doses (low (the initial dose) vs high (escalated doses) at the time of initiation of the high dose). The number of TEAEs per patient-year of exposure will also be presented, where patient years will be the sum of treatment duration in a column converted to years.

All TEAEs will be summarized by the *Medical Dictionary for Regulatory Activities* (MedDRA) System Organ Class (SOC) and Preferred Term (PT). The dictionary version will be established and documented during the blinded data review meeting prior to lock of the data.

Subjects experiencing more than one TEAE by SOC and PT will only be counted once at the preferred terminology level in AE frequency tables, but each unique TEAE will be included in the total number of TEAEs (where provided) for each SOC and PT. The overall summary for SOC and PT will be presented for each study drug arm, the mutation positive placebo arm, and the mutation negative placebo arm. The summary will also be reported by doses (low (the initial dose) vs high (escalated doses) at the time of initiation of the high dose).

In summaries presented by SOC and PT, SOC will be sorted by alphabetical order; within SOC, PT will be sorted according to the subject incidence rate of the active treatment arm.

The number and percentage of subjects reporting TEAEs will be summarized by treatment arm, and by SOC and PT.

Serious Adverse Events (SAEs)

A SAE is any AE which meets any of the following criteria:

- Death of subject
- Life-threatening

- Inpatient hospitalization or prolongation of existing hospitalization
- Persistent or significant disability/incapacity
- Congenital anomaly/birth defect
- Other

The SAE will be presented by a listing. The subject's ID number, treatment arm (without including eligible DIAN-OBS subjects), SOC, PT and verbatim term, SAE onset/stop date and SAE criteria will be included in the listing.

Relationship of Adverse Events to Study Drug

The relationship of an AE to a study drug will be listed as the following per the guidance provided in Protocol Section 7.3:

- Definite
- Probable/Likely
- Possible
- Unlikely
- Definitely Not

Events will be classified as either related (including definite, probable/likely, possible, or missing relationships) or not related (including unlikely, definitely not relationships). The number and percentage of subjects with TEAEs related to study drugs or imaging agents will be summarized by dichotomous relationship, treatment arm (without including eligible DIAN-OBS subjects), and by SOC and PT.

Adverse Events Leading to Death and Discontinuation

AEs that lead to discontinuation and deaths will be presented by a listing. The subject's ID number, treatment arm, the TEAE that caused the discontinuation, and date of discontinuation will be included in the listing. Treatment discontinuation AEs and study discontinuation AEs will be listed separately.

TEAE Severity

The severity of a TEAE is defined as the following:

-
- Mild: An event that is transient and easily tolerated by the subject; requires minimal or no treatment and does not interfere with the subject's daily activities.
 - Moderate: an event that causes the subject discomfort and may cause some interference in the subject's usual activities.
 - Severe: an event that causes considerable interference with the subject's usual activities, may require drug therapy or other treatment, and may be incapacitating or life-threatening.

The number and percentage of subjects with a severe TEAE will be summarized by maximum severity (if a TEAE has multiple levels of severity over time), treatment arm, and by SOC and PT.

Outcome

The outcome of a TEAE can be one of the following (from best to worst with "unknown" as an independent category):

- Recovered/Resolved
- Recovering/Resolving
- Not Recovered/Not Resolved
- Recovered/Resolved with sequelae
- Fatal
- Unknown

The outcome will be considered as categorical and will be summarized by treatment arm. If a subject has multiple outcomes within a SOC/PT, the worst outcome will be included in the summary with "unknown" as an independent category.

Action Taken due to TEAE

Action Taken with study treatment can be one of the following:

- Dose not changed
- Dose increased
- Dose reduced
- Dose held
- Administration interrupted
- Drug withdrawal

- Not applicable
- Unknown

The action taken with study treatment will be summarized by treatment arm (without including eligible DIAN-OBS subjects), action taken categories, SOC and PT. If multiple actions are taken for a subject, then each action will be counted in its own category. If the same action is taken multiple times for a subject, then the same action will be counted as many times in its category. The summary will be conducted for each action.

When dose escalation is carried out for any study drug, the dose will increase or be held stable before increasing to a higher dose. The dose change during the dose escalation process will not be counted as the action taken due to TEAE.

Other Causes of Adverse Events

The other causes of adverse events include:

- AE involving the injection/infusion site
- AE occurring due to administration of florbetapir [¹⁸F] AV-45 PET
- AE occurring due to administration of PIB
- AE occurring due to administration of FDG
- AE occurring due to administration of [¹⁸F] AV-1451 Tau PET

The relationship of an AE to these causal factors will be presented in the same manner as described for relationship to study drug. The other causes of AEs will be summarized by treatment arm, by causes and by relationship.

13.3 Amyloid-related Imaging Abnormalities (ARIAs)

The number and percentage of subjects with MRI scan (including annual, safety, and dose titration MRIs) conducted will be summarized by visit and by treatment arm for each type of MRI finding.

ARIA can occur as either cerebral edema (ARIA-E) or as hemorrhages (ARIA-H), typically microhemorrhages, but larger hemorrhages and frank infarction have also been reported. MRI scans will be analyzed for ARIA changes at the Mayo Clinic Aging and Dementia Imaging

Laboratory. The number of microhemorrhages (ARIA-H, including both hemorrhages and hemosiderin deposits) and size of areas of edema (ARIA-E) will be monitored at entry and throughout the trial.

Frequencies, percentages, and number of events per patient-year of ARIA-E and ARIA-H will be summarized by treatment arm (without including eligible DIAN-OBS subjects), by dose (all doses), and by visit. The number of ARIA-H and ARIA-E will be categorized (1, 2 to 4, 5+, or no presence) and summarized by treatment arm (without including eligible DIAN-OBS subjects) and by visit. The size of ARIA-E will be summarized using mean (SD) by treatment arm (without including eligible DIAN-OBS subjects) and by visit. A listing of all ARIA-E findings will be produced for all subjects who have an incidence of ARIA-E at any assessment. The listing will include the number of definite findings for ARIA-E, the size of ARIA-E, the number of days since treatment start, the current active drug dose, and the number of days since start of the current active drug dose.

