7.4 Safety Analysis Population for DIAN-TU-001 Subjects

The safety analysis population includes all subjects who have consented to participate and have received at least one dose of any study drug or placebo. Subjects in the safety analysis population will be allocated into treatment arms "as treated" in the event that randomized treatment is incorrectly dispensed and continues to be the treatment during the follow-up. Subjects in the safety analysis population will be allocated into treatment arms "as initially treated" in the event that a subject incidentally receives a dose or multiple doses of an incorrect treatment but receives the correct treatment for the other doses; this subject's treatment

assignment will not be changed because of the incorrectly administered dose. For any study drug, this population includes the mutation positive subjects on the active treatment, mutation positive subjects on placebo (including the direct placebos, and the concurrently randomized placebos), and mutation negative subjects on placebo (including only the direct placebos and concurrently randomized placebos).

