2.2 Treatment Administration Schedule and Duration

All subjects start at a dose of 225 mg of study drug administered subcutaneously every 4 weeks. Following the approval of Amendment 5, all subjects will sign the new ICF and initiate dose escalation per protocol starting at the 450 mg dose level ([Table 17](#)).

Table 17: DIAN-TU-001 Titration Schedule: Gantenerumab

INITIAL DOSE	TITRATION STEP #1	TITRATION STEP #2	TITRATION STEP #3	TITRATION STEP #4	STABLE DOSE

 •225 mg every 4 weeks until up titration initiated •MRI Frequency^a 	
 •450 mg •450 mg •Safety MRI: 1 week after 2nd 450 mg dose, before increase to 675 mg^b 	
 •675 mg •675 mg •Safety MRI: 1 week after 2nd 675 mg dose, before increase to 900 mg^b 	
 •900 mg •900 mg •Safety MRI: 1 week after 2nd 900 mg dose, before increase to 1200 mg^b 	
 •1200 mg •1200 mg •Safety MRI: 1 week after 2nd 1200 mg dose; if all clear, then a safety MRI will be done after every 3rd dose^b. 	
 •1200 mg dose every 4 weeks •Safety MRI following a week after every 3rd dose unless an annual visit is the next visit in which case the vMRI can be used.^c

- ^a Safety MRI will be scheduled before the first dose (baseline scan for safety reads done at V2) and then about 1 week after dose 2; dose 4; dose 6; dose 9; dose 17 and dose 22. Additional safety MRIs are done as part of the volumetric MRI at the annual assessments before dose 14 (V15, week 52), dose 27 (V28, week 104), dose 40 (V41, week 156), and V54 (week 208). This schedule will be followed until up titration is initiated.
- ^b A safety MRI will be scheduled 1 week after the second dose of each titration step, unless otherwise indicated by the ARIA-E and ARIA-H management algorithms (Section 1.15). If an annual visit follows the second dose of a titration step, the annual MRI assessment (vMRI) can fulfill this requirement as long as the MRI reading is reviewed prior to dosing at that visit.

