- ^c The titration schema was designed to reach the target dose of 1200 mg every 4 weeks, however, the target dose may not be achieved as otherwise dictated ARIA-E and ARIA-H management algorithms (Section 1.15) or more conservative action by the site principal investigator/sponsor. Once a subject reaches their stable dose (defined as the maximum dose the subject will remain at for the duration of the trial) safety MRIs will follow every 3rd dose (or approximately every 3 months) unless otherwise indicated by the algorithm. If the next visit is an annual visit, the annual assessment (vMRI) can fulfill this requirement.

For the primary analysis, the treatment duration will last until the last subject enrolled has reached 48 months of treatment after initial randomization. Because of the length of trial enrollment, there will be subjects with greater than 48 months exposure with a maximum, estimated, duration near 78 months.

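### By-dose ARIA rates per patient-year mix dose with MRI surveillance, because the gantenerumab scan schedule changes with dose phase

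*SAP*

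**What the plan says.** SAP Section 13.3 commits to a rate measure, events per patient-year, and says that ARIA-E and "ARIA-H will be summarized by treatment arm (without including eligible DIAN-OBS subjects), by dose (all doses), and by visit". The SAP defines patient-years only once, in Section 13.2 for treatment-emergent adverse events, where "patient years will be the sum of treatment duration in a column converted to years". It gives no separate definition for ARIA, so the natural denominator is time on treatment, not scans.

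Appendix VII, Section 2.2, Table 17 and its footnotes set three scan cadences for gantenerumab:

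- **225 mg:** safety scans before the first dose, "then about 1 week after dose 2; dose 4; dose 6; dose 9; dose 17 and dose 22", plus annual scans at weeks 52, 104, 156 and 208, until up-titration starts.
- **Titration:** "A safety MRI will be scheduled 1 week after the second dose of each titration step".
- **Stable dose:** "safety MRIs will follow every 3rd dose (or approximately every 3 months").

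Section 13.3 also counts subjects scanned, but by visit and arm, not by dose. Its ARIA-E listing shows the current dose and the days on that dose. The SAP does not say to which dose a lesion first seen after a dose change belongs.

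**The concern.** ARIA is counted only when a scan is read. An ARIA-E that appears and resolves between two scans is never recorded, so a dose phase with sparse scans records fewer events per patient-year than one with dense scans, even at the same true incidence. Because scan frequency is tied to dose phase, the by-dose table cannot separate the two effects.

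A second route does not need transient lesions. Table 17 as shown lists no scan at the start of titration; the first is one week after the second 450 mg dose. A lesion that arose late in a long 225 mg scan gap may be first seen, and counted, at 450 mg.

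At stake is the descriptive reading of ARIA risk by dose after escalation.

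**Working it through.** The SAP states no ARIA rate to reproduce, so the check starts from Table 17.

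**Scan times.** Doses are 4 weeks apart, so dose k falls at week 4(k − 1). Doses 14, 27 and 40 then fall at weeks 52, 104 and 156, as footnote a states. Scans one week after doses 2, 4, 6, 9, 17 and 22 fall at weeks 5, 13, 21, 33, 65 and 85. With the annual scans, the gaps at 225 mg in weeks are:

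- year 1: 5, 8, 8, 12, 19 (5 scans)
- year 2: 13, 20, 19 (3 scans)
- years 3 and 4: 52 each (1 scan per year)

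Titration has one scan per two doses: 52/8 = 6.5 per year. Stable dose has one per three doses: 52/12 = 4.33 per year.

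**Time at 225 mg.** Appendix VI scenario F assumes the dose change after 3 years for 14 subjects, 2 years for 111 and 1 year for 16. (These sum to 141, not the 140 used elsewhere; the effect here is negligible.) Patient-years: 14×3 + 111×2 + 16×1 = 280, made up of 141 in year 1, 125 in year 2 and 14 in year 3. Scans: 14×9 + 111×8 + 16×5 = 1094. Average: 1094/280 = 3.91 per patient-year.

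**Share of episodes seen.** With a constant true rate and an episode visible for D weeks, the share seen is the sum of min(gap, D) over the scan gaps, divided by total time. D is assumed, and each phase is treated as steady state. For D = 8:

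- year 1: (5 + 8 + 8 + 8 + 8)/52 = 37/52 = 0.71
- year 2: 24/52 = 0.46
- year 3: 8/52 = 0.15
- pooled 225 mg: (141×37 + 125×24 + 14×8)/(280×52) = 8329/14560 = 0.572
- titration: 8/8 = 1.00; ratio 1/0.572 = 1.75
- stable: 8/12 = 0.667; ratio 0.667/0.572 = 1.17

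The same formula for other durations gives:

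| D (weeks) | Pooled 225 mg | Titration | Stable | Titration / 225 mg | Stable / 225 mg |
|---|---|---|---|---|---|
| 4 | 4376/14560 = 0.301 | 0.500 | 0.333 | 1.66 | 1.11 |
| 8 | 0.572 | 1.00 | 0.667 | 1.75 | 1.17 |
| 12 | 11013/14560 = 0.756 | 1.00 | 1.00 | 1.32 | 1.32 |
| 16 | 12758/14560 = 0.876 | 1.00 | 1.00 | 1.14 | 1.14 |
| 20 | 14112/14560 = 0.969 | 1.00 | 1.00 | 1.03 | 1.03 |

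**Direction.** Against first-year 225 mg alone, the stable-dose ratio is 0.333/(20/52) = 0.87 at 4 weeks and 0.667/(37/52) = 0.94 at 8 weeks, so it reverses.

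**First 450 mg scan.** If the first 450 mg dose is given x weeks after the last 225 mg scan, the first titration scan closes an interval of x + 5 weeks, of which x were at 225 mg. When x is large, 225 mg lesions are counted at 450 mg. When x = 0 (titration starting at an annual scan), the interval is only 5 weeks within an 8-week step. The 450 mg row alone then has a share of 5/8 = 0.625 for D of 5 weeks or more, and ratios to 225 mg of 1.09, 0.83 and 0.71 at 8, 12 and 16 weeks.

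**Would a per-scan rate fix it?** New episodes per scan equal the ratio above times 3.91/6.5 for titration against 225 mg. This gives 1.00, 1.05, 0.79, 0.69 and 0.62 at 4, 8, 12, 16 and 20 weeks. It is neutral only while episodes are no longer than the scan gap. Beyond that it understates the densely scanned doses.

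**The case against.** The strongest reply is that the size rests on inputs that are not trial facts. ARIA-E duration is nowhere in the document. The scenario F times are one simulation assumption applied to both drugs, although Section 3.7 ties escalation to Amendment 5 for gantenerumab and Amendment 7 for solanezumab. Extra scans driven by the ARIA management algorithms are not shown and are not counted here. Section 13.3 is descriptive, with no test of dose, and the SAP also gives ARIA by visit and the ARIA-E listing. All of this stands. It limits the size and weight of the point, but none of it adjusts the by-dose rate.

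Three stronger readings are tempting and not supported:

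- **Higher doses must show more ARIA-E.** This needs episodes that resolve between scans and enough time at 225 mg beyond year 1. The calculation shows reversals.
- **The inflation could be 6.5-fold.** For 8-week episodes, titration against third-year 225 mg does give 52/8 = 6.5. But the table is by dose, not by dose and year, and year 3 is 14 of 280 patient-years (5%) under scenario F.
- **Pooled placebo is a biased comparator.** Section 7.4 does pool "mutation positive subjects on placebo (including the direct placebos, and the concurrently randomized placebos"). But Section 3.6 only leaves MRI frequency to drug-specific protocol appendices. The solanezumab schedule is not shown, and Section 10 already includes a mutation positive direct placebo group in the descriptive safety outputs. This can be raised only conditionally. Active against direct gantenerumab placebo is largely protected, because all subjects enter the escalation and its scheduled scans.

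**Conclusion.** The point holds as a confounding of dose with surveillance in the by-dose ARIA rates, not as a bias of fixed sign. With equal true incidence, visible durations of 4 to 16 weeks and scenario F timing, titration doses can show about 1.1 to 1.75 times the pooled 225 mg rate, and stable dose about 1.1 to 1.3 times. The effect nearly disappears at 20 weeks, the longest gap in the first two years at 225 mg; third-year gaps of 52 weeks leave a small remainder. The missing rule for assigning a lesion to a dose is a separate gap that also affects persistent ARIA-H. No efficacy conclusion or hypothesis test is affected. The correction is worth making because it is cheap and because a reader could otherwise take a scan-frequency artefact for a dose effect.

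**What to change.** Amend Section 13.3, analysis only:

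1. Report MRIs read per patient-year by dose beside the ARIA rates, and state the patient-year denominator for ARIA.
2. Tabulate the direct gantenerumab placebo subjects by the same blinded titration step, so that each dose is set against placebo under the same scheduled scans.
3. For ARIA-H and first ARIA-E, add interval-censored incidence between consecutive scans, assigned to the dose or doses given in that interval. State how a lesion first seen after a dose change is assigned.
4. Give new ARIA-E per MRI read only as a supplement, because it understates densely scanned doses when episodes outlast the scan gap.
5. Keep the per-patient-year figures, with a note on scan frequency.

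The cost is SAP wording and one or two extra tables. The Section 13.3 listing already draws on scan findings, current dose and days on dose. The drawback is small placebo cells: about 17 direct placebo subjects, against 34 pooled. The MRI schedule and dosing do not change.
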